10.3.1. Liver chemistry stopping criteria and Required Actions and Follow-up Assessments

Study treatment or Investigational Product must stop immediately when participant meets one of the criteria described in below:

Liver Chemistry Stopping Criteria - Liver Stopping Event				
If baseline ALT ≤ 1.5x ULN				
ALT-absolute	$ALT \ge 8x ULN$			
ALT Increase	ALT \geq 5x ULN but <8x ULN persists for \geq 2 weeks (with bilirubin <2x ULN and no signs or symptoms of acute hepatitis or hypersensitivity)			
Bilirubin ^{1, 2}	ALT \ge 3x ULN and bilirubin \ge 2x ULN (>35% direct bilirubin)			
Cannot Monitor	ALT \ge 5x ULN but <8x ULN and cannot be monitored every 1 - 2 weeks			
Symptomatic ³	$ALT \ge 3x$ ULN with symptoms (new or worsening) believed to be related to liver injury or hypersensitivity			
	If baseline ALT > 1.5x ULN			
ALT-absolute	$ALT \ge 5x \text{ baseline OR} > 500 \text{ U/L}$ (whichever occurs first)			
ALT Increase	ALT \ge 3x baseline but <5x baseline persists for \ge 2 weeks (with bilirubin <2x ULN and no signs or symptoms of acute hepatitis or hypersensitivity)			

Liver Chemistry Stopping Criteria - Liver Stopping Event			
Bilirubin ^{1, 2}	ALT \ge 3x baseline OR > 300 U/L (whichever occurs first) and bilirubin \ge 2x ULN		
Cannot Monitor	ALT \ge 3x baseline but <5x baseline and cannot be monitored every 1 - 2 weeks		
Symptomatic ³	ALT \ge 3x baseline and symptoms (new or worsening) believed to be related to liver injury or hypersensitivity.		
1. Serum bilirubin fractionation should be performed if testing is available. If serum bilirubin			

- fractionation is not immediately available, discontinue study intervention for that participant if ALT \ge 3x ULN and bilirubin \ge 2x ULN. Additionally, if serum bilirubin fractionation testing is unavailable, record presence of detectable urinary bilirubin on dipstick, indicating direct bilirubin elevations and suggesting liver injury.
- 2. All events of ALT ≥3x ULN and bilirubin ≥2x ULN (>35% direct bilirubin) must be reported as an SAE (excluding studies of hepatic impairment or cirrhosis); INR measurement is not required, and the threshold value stated will not apply to participants receiving anticoagulants.
- 3. New or worsening symptoms believed to be related to liver injury (such as fatigue, nausea, vomiting, right upper quadrant pain or tenderness, or jaundice) or believed to be related to hypersensitivity (such as fever, rash or eosinophilia).

Required Actions and Follow up Assessments following ANY Liver Stopping Event			
Actions	Follow Up Assessments		
 Immediately discontinue study intervention. Report the event to the Medical Monitor within 24 hours. Complete the liver event eCRF and complete an SAE data collection tool if the event also meets the criteria for an SAE². Complete the liver imaging and/or liver biopsy eCRFs if these tests are 	 Make every attempt to carry out liver event follow-up assessments at the central laboratory as described below: Viral hepatitis serology, including: Hepatitis A immunoglobulin M (IgM) antibody; HBsAg and hepatitis B core antibody; Hepatitis C RNA; 		
 performed. Perform liver event follow up assessments. Monitor the participant until liver chemistries resolve, stabilise, or return to within baseline (see MONITORING below). 	 Hepatitis E IgM antibody. Cytomegalovirus IgM antibody. Epstein-Barr viral capsid antigen IgM antibody (or if unavailable, obtain heterophile antibody or monospot testing). 		

n • d A J TAU • ANV T : . 4~ f~11 C1 .

Required Actions and Follow up Assessments following ANY Liver Stopping Event			
Actions	Follow Up Assessments		
• Do not restart participant with study intervention unless allowed per protocol and VSLC approval is granted (refer to Section 10.3.2.2).	Syphilis screening.Drugs of abuse screen, including alcohol.		
• If restart is not allowed or not granted , permanently discontinue study intervention and may continue participant in the study for any protocol specified follow up assessments.	• Serum acetaminophen adduct HPLC assay (quantifies potential acetaminophen contribution to liver injury in participants with definite or likely acetaminophen use in the preceding week [James, 2009]). The site must contact the Medical Monitor when this test is required.		
 MONITORING: Make every reasonable attempt to have participants return to clinic within 24 hours for repeat liver chemistries 	 Blood sample for pharmacokinetic (PK) analysis, obtained within 60 hours of last dose⁴. 		
(include ALT, AST, alkaline phosphatase, bilirubin) and perform liver event follow up assessments.	• Serum CPK and lactate dehydrogenase (LDH).		
 Monitor participants twice weekly until liver chemistries resolve, stabilise or return to within baseline. A specialist or hepatology consultation is recommended. 	• Fractionate bilirubin, if total bilirubin ³ 1.5x ULN.		
	• Obtain complete blood count with differential to assess eosinophilia.		
	• Anti-nuclear antibody, anti- smooth muscle antibody, Type 1 anti-liver kidney microsomal antibodies, and quantitative total immunoglobulin G (IgG or gamma globulins).		
	• Gamma glutamyl transferase [GGT], glutamate dehydrogenase [GLDH], and serum albumin		
	• International normalized ratio (INR)		
	 Liver imaging (ultrasound, magnetic resonance, or computerised tomography) and /or liver biopsy to evaluate liver diseaseⁱ complete Liver Imaging 		

Required Actions and Follow up Assessments following ANY Liver Stopping Event			
Actions	Follow Up Assessments		
	and/or Liver Biopsy eCRF forms.		
	• Record the appearance or worsening of clinical symptoms of liver injury, or hypersensitivity, fatigue, decreased appetite, nausea, vomiting, abdominal pain, jaundice, fever, or rash as relevant on the AE report form.		
	• Record use of concomitant medications on the concomitant medications report form including acetaminophen, herba remedies, other over the counter medications.		
	• Record alcohol use on the liver event alcohol intake eCRF.		

- ---

CPK - creatine phosphokinase

1. Serum bilirubin fractionation should be performed if testing is available. If serum bilirubin fractionation is not immediately available, discontinue study intervention for that participant if ALT $\ge 3x$ ULN and bilirubin $\ge 2x$ ULN. Additionally, if serum bilirubin fractionation testing is unavailable, record presence of detectable urinary bilirubin on dipstick, indicating direct bilirubin elevations and suggesting liver injury. 2. All events of ALT $\ge 3x$ ULN and bilirubin $\ge 2x$ ULN (>35% direct bilirubin) must be reported as an **SAE (excluding studies of hepatic impairment or cirrhosis)**; INR measurement is not required and the threshold value stated will not apply to participants receiving anticoagulants

3. New or worsening symptoms believed to be related to liver injury (such as fatigue, nausea, vomiting, right upper quadrant pain or tenderness, or jaundice) or believed to be related to hypersensitivity (such as fever, rash or eosinophilia)

4. Record the date/time of the PK blood sample draw and the date/time of the last dose of study intervention prior to blood sample draw on the eCRF. If the date or time of the last dose is unclear, provide the participant's best approximation. If the date/time of the last dose cannot be approximated OR a PK sample cannot be collected in the time period indicated above, do not obtain a PK sample. Instructions for sample handling and shipping are in the SRM.

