- f) Height and body mass index (BMI) are collected at screening only.
- g) A (-) urine pregnancy test is required prior to oral lead-in at day 1 and prior to any injection and as required by Medical Monitor after a treatment interruption. A (+) urine test should be confirmed with a stat serum test. If (+), participant will need to be withdrawn. A Serum pregnancy test should be performed at any time pregnancy is suspected by the Investigator. Pregnant participants who remain in the study do not need pregnancy testing for the duration of the pregnancy see Appendix 15: Information and Guidance for Managing Pregnant Participants.
- h) Plasma for storage samples are collected for possible future analyses. Can be used for back-up in cases of loss/damage in transit, geno/pheno analyses for virologic failures. Only for women becoming pregnant and continuing on CAB LA+RPV LA as if pregnant a plasma HIV-1 RNA test and plasma for storage samples at Month 6 and Month 10 visits are required.
- i) All injections are 1 x CAB LA 600 mg IM + 1 x RPV LA 900 mg IM. Doses 1 and 2 are one month apart. Subsequent injections beginning at Dose 3 are every two months. The injections should be spaced approximately 2 cm from one another and from the site of any previous injection and/or any injection site

reaction. Bring RPV LA to approximately room temperature prior to injecting. Time and location of injection (right or left) as well as needle length used will be collected in the eCRF. IM dosing is expected to occur on the same date of the month as determined by IM Dose 1 visit date, this is the Target Date; where possible, this first injection should be performed within 2 hours of taking the last oral regimen dose. For Dose 2, a dosing window of +0 / -7 days from the target visit date is stipulated. A (+ or -) 7-day window from the target date visit is stipulated for IM dosing beginning at Dose 3. All decisions regarding dose interruption/ resumption must be discussed with the Medical Monitor in advance.

- Length of study visit from arrival until departure from clinic will be evaluated. Participant's time of arrival, actual start time of the appointment, and actual end time of the appointment will be collected in the eCRF.
- k) Questionnaires should be completed before receiving the injections.

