HIV-1 infected participants who meet all eligibility criteria will be switched from their pre-baseline regimen to an oral regimen (CAB 30 mg + RPV 25 mg once daily) during the **oral lead-in phase**. Participants will return to the clinic, and if laboratory and clinical evaluations continue to support progression into the **injection treatment phase** of the study, will take the last dose of their oral regimen (CAB 30 mg + RPV 25 mg) and receive the first dose of CAB LA (600 mg) + RPV LA (900 mg) injections on the same day (Month 1). The participant will receive the second injections CAB LA (600 mg) + RPV LA (900 mg) one month later (Month 2). All subsequent injections will occur every two months thereafter (Month 4, Month 6, etc) for a total of 7 doses of CAB LA

and RPV LA (Table 7). The total length of the treatment phase is approximately one year.

Table 7 Dosing Regimen

Oral Lead-in to End of Study ⁺		
CAB + RPV Oral Lead-In		
Oral Lead-in (Day 1 to Month 1)	• Take one tablet of CAB 30 mg + RPV 25 mg once daily	
two once daily tablets taken with food		
CAB LA + RPV LA Injections		
Dose 1 (Month 1)	Receive last dose of oral CAB + RPV regimen	
	 Receive CAB LA 600 mg given as 1 X 3 mL IM injection 	
	 Receive RPV LA 900 mg given as 1 X 3 mL IM injection 	
Dose 2 to Dose 7 (Month 2- End of Study ⁺)	 Receive CAB LA 600 mg given as 1 X 3 mL IM injection 	
two 3 mL injections every two months	 Receive RPV LA 900 mg given as 1 X 3 mL IM injection 	
+Until after dose 7 (Month 12) when locally approved and commercially available, the participant no longer derives clinical benefit, the participant meets a protocol-defined reason for discontinuation or until development of CAB LA or RPV LA is terminated		

The dosing window for the second injections will be +0/-7 days from the projected target date (target date is established at Month 1). All subsequent injection windows (starting with Dose 3) will be +7/-7 days from the projected target date. Doses outside of the window *may* be allowed with prior Medical Monitor approval.

Participants will continue CAB LA + RPV LA until:

- After dose 7 and when the study intervention is locally approved and available for the Investigator to prescribe. Note if intervention is not locally approved at dose 7 they will continue into the Extension Phase (see Section 6.8).
- the participant no longer derives clinical benefit
- the participant meets a protocol-defined reason for discontinuation

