6.5.3. IM Dosing

Participants receiving CAB LA and/or RPV LA are anticipated to be at risk for development of virologic resistance if antiretroviral therapy is interrupted. The time period during which participants are at risk for development of virologic resistance may be determined by the period between when drug levels fall below therapeutic values and when they fall below levels which exert selective pressure on HIV. This time period will vary by ART agent and is dependent upon effective concentration, inhibitory concentration, and half-life. Plasma concentrations of both LA drugs may be measurable for more than one year following IM injections. Any interruption in IM dosing should be discussed with the Medical Monitor. Investigators should ensure that the participant initiates alternative highly active ART to minimize the risk of developing resistance as concentrations of and RPV decline over time.

CAB LA + RPV LA dosing for participants transitioning from oral CAB + RPV is as follows:

All injections should be planned as single injections per drug.

Target Date

The patient's 'target date' is determined by their first injection date and ideally is the same date for every injection. For example, if the1st dose (Month 1) is January 15th, then dose 2 (Month 2) will be February 15th, and dose 3 (Month 4) will be April 15th, etc.

Since the first injection visit (Month 1) will determine the future injection visit schedule for participants and ideally be between the 1st and 28th day of the month. Planning for the first injection visit date (within allowed visit windows) should take into consideration the availability of the participants to adhere to future visit windows (planned vacations, business trips, *etc.*).

Treatment Injections- Months 1 and 2 -one month apart

Participants will take the last dose of their oral (CAB 30 mg + RPV 25mg) and receive the first CAB LA (600mg) + RPV LA (900mg) injections (within 2 hours of the final oral dose of CAB + RPV).

The second dose (CAB LA 600mg + RPV LA 900mg) will be administered one month later (preferable on the same target date as Dose 1). The dosing window for Dose 2 allows administration -7days of the proposed visit date but not later.

Treatment Injections- Months 4- Q2M dosing

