Subsequent injections (Dose 3 through 7: CAB LA 600mg + RPV LA 900mg) occur every 2 months. The dosing window is \pm 7days. The Medical Monitor must be contacted to discuss individual participant case management if a dose must be administered outside of the window.

Nursing Visits for IM Dosing

Qualified healthcare professionals (HCPs) trained on study procedures can administer IM injections outside of the study clinic setting (e.g. home, nursing facility, hospital), assuming this can be done safely, without compromising investigational product preparation/handling/storage/accountability requirements and done in accordance with local requirements. Approval by the medical monitor, the study team and IRB/EC RA as locally required are needed for nursing visits. In cases of nursing visits, where feasible, all assessments should also be performed as per schedule of activity Section 1.3 (Table 1). See the Home-visit Handbook for procedural detail on home visits.

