8.5.5.4. Action to be Taken if Pregnancy Occurs

Any pregnancy that occurs during study participation must be reported using a clinical trial pregnancy form. The investigator should inform GSK within 24 hours of learning of the pregnancy and should follow the procedures outlined in Section 10.15.

Pregnant participants who elect to continue in the study and receive CAB + RPV LAmust sign a pregnancy specific ICF addendum. Cabotegravir and rilpivirine are detected in systemic circulation for up to 12 months or longer after discontinuing injections of CAB + RPV LA; therefore, consideration should be given to the potential for fetal exposure during pregnancy and should be discussed between the study participant and the study PI.

Participants who become pregnant during the study and elect to continue in the study and receive CAB+RPV LA, will have additional PK samples collected to monitor cabotegravir and rilpivirine exposure levels throughout the pregnancy (see Section 10.15) and at the time of delivery.

The pregnancy must be followed up to determine outcome (including premature termination) and status of mother and child(ren). Pregnancy complications and elective terminations for medical reasons must be reported as an AE or SAE. Abnormal pregnancy outcomes (e.g., spontaneous abortion, fetal death, stillbirth, congenital anomalies, ectopic pregnancy) are considered SAE.

Any SAE occurring in association with a pregnancy brought to the investigator's attention after the participant has completed the study and considered by the Investigator as possibly related to the study intervention, must be promptly reported to ViiV/GSK.

GSK's central safety department will also forward this information to the Antiretroviral Pregnancy Registry. The international registry is jointly sponsored by manufacturers or licensees of ARV products. Additional information and a list of participating manufacturers/licensees are available from http://apregistry.com/

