8.6. Pharmacokinetics

Pharmacokinetic samples may be collected in cases of maladministration, liver events, to follow-up pregnancy, at plasma HIV 1 RNA retest of SVF, or as directed by the medical monitor.

Pregnant participants will have additional PK samples collected during the duration of the pregnancy. See Appendix 15: Information and Guidance for Managing Pregnant Participants

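### The 60-hour limit on liver-event PK sampling fits daily tablets but covers about 4% of a two-month injection interval, and it conflicts with Protocol Sections 8.4.4 and 8.6

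*Protocol*

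**What the plan says.** Protocol Section 10.3.1 lists the follow-up assessments after any liver stopping event. One item is "Blood sample for pharmacokinetic (PK) analysis, obtained within 60 hours of last dose". Footnote 4 to that list covers the case where the time of the last dose cannot be approximated, or where "a PK sample cannot be collected in the time period indicated above, do not obtain a PK sample". Neither the item nor the footnote distinguishes oral from long-acting dosing.

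The regimen has both. The lead-in is "an oral regimen (CAB 30 mg + RPV 25 mg once daily" for about a month (Section 4.3.3). For the injections, "Doses 1 and 2 are one month apart" (Section 1.3, Table 1 footnote i), and then "Subsequent injections (Dose 3 through 7: CAB LA 600mg + RPV LA 900mg) occur every 2 months" (Section 6.5.3). On persistence, Section 6.5.3 states: "Plasma concentrations of both LA drugs may be measurable for more than one year following IM injections". Section 8.5.5.4 is similar: "Cabotegravir and rilpivirine are detected in systemic circulation for up to 12 months or longer after discontinuing injections".

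Two other places deal with PK sampling for liver events. Section 8.6 says: "Pharmacokinetic samples may be collected in cases of maladministration, liver events, to follow-up pregnancy", and it ends by adding any case the medical monitor directs. The laboratory table in Section 8.4.4 says much the same. Neither sets a time limit.

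**The concern.** A 60-hour window suits a drug taken every day. Applied to an injection given every two months, it turns away samples that would still carry information, because by the protocol's own account the drug remains in plasma long after 60 hours. A site that follows the liver-event instructions would not sample a participant who develops symptoms three weeks after an injection. A site that follows Section 8.6 could sample the same participant.

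Drug-induced liver injury is the first risk listed for CAB in Section 2.3.1, and the protocol itself puts a PK sample on the liver-event list. If the 10.3.1 wording is followed, some liver events on long-acting drug will have no concentration value. Those values will then be absent from the SAP's concentration listings (Listings 47 and 48). If practice differs by site, whether an exposure value exists will depend on which section the site read.

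**Working it through.** The documents state no coverage percentage, so there is no plan figure to reproduce. The inputs are the 60-hour window (10.3.1), the dosing intervals (4.3.3, 6.5.3 and Table 1 footnote i) and the timing of chemistry (Table 1).

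**Share of a dosing interval covered** = 60 h / (interval in days × 24 h)

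| Interval | Hours | Share covered |
|---|---|---|
| Daily oral dosing | 24 | 100% |
| Dose 1 to Dose 2, one month (mean 30.4 days) | 730.5 | 60/730.5 = 8.2% (8.1–8.9% for 31–28 days) |
| Two months (mean 60.9 days) | 1,461 | 60/1,461 = 4.1% (4.0–4.2% for 62–59 days) |
| Two months, interval 7 days longer or shorter (69 or 54 days) | 1,656 or 1,296 | 3.6% or 4.6% |

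From Month 1 to Month 12 there are six intervals: 6 × 2.5 days / 334.8 days = 4.5%. With the fully covered lead-in month added, Day 1 to Month 12 gives (30.4 + 15) / 365.25 = 12.4%.

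**From time covered to events covered.** If events were detected evenly over a two-month interval, 100% − 4.1% = about 96% would fall outside the window. Detection is not even, because scheduled chemistry in the injection period is at Months 1, 2, 4, 8 and 12, all injection visits. Suppose an event is found on chemistry drawn on an injection day and the injection is given. The delay to sampling is then laboratory turnaround plus return time. Section 10.3.1 aims for return within 24 hours. Turnaround is not stated, so these values are assumptions:

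- 24 h + 24 h = 48 h, inside the window
- 36 h + 24 h = 60 h, at the limit
- 48 h + 24 h = 72 h, outside

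If a share s of events is sampled in time by this route and the rest are spread evenly, coverage = s + (1 − s) × 60/1,461:

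| s | Coverage |
|---|---|
| 0 | 4.1% |
| 0.25 | 28% |
| 0.5 | 52% |
| 0.75 | 76% |

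**Events that tend to miss the window without any evenness assumption:**

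- *Persistent ALT elevation.* One stopping criterion in 10.3.1 needs the elevation to last two weeks or more. Under 7.1.1, dosing may continue meanwhile, with chemistry repeated every two weeks. If the first abnormal value was drawn on an injection day, the event is declared at least 14 days (336 h) after that injection. It meets 60 hours only if a further injection happened to come shortly before.
- *Symptomatic events.* These can arise at any time between visits, and Months 6 and 10 have no scheduled chemistry.
- *Long-term follow-up.* Section 10.6.5.1 applies the liver criteria in the follow-up phase. Visits with chemistry are at months 3, 6, 9 and 12 after the last injection. Footnote 4 counts from the last dose of study intervention, read here as the last injection because follow-up HAART is not trial material (6.1). On that reading every scheduled detection is outside 60 hours.

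**The case against.** The strongest reply is that the protocol as a whole does not ban the sample. Sections 8.4.4 and 8.6 allow it, including at the medical monitor's direction, and 10.3.1 requires the medical monitor to be told of a stopping event within 24 hours. Someone able to order a sample is therefore always involved. This stands: the prohibition belongs to 10.3.1 and footnote 4 only. It does not settle the matter, because 8.4.4 and 8.6 say samples may be taken, the liver-event instructions say not to, and no text says which governs.

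The second reply is that events will not be detected evenly, for the reasons shown in the working. This also stands. In addition, an abnormality on Month 1 chemistry falls on the day of the last oral dose and the first injection.

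The third is that little depends on these values. SAP Section 9 only lists whatever concentrations are available, and no endpoint uses them. Section 2.3.1 puts transaminitis below 1% of CAB programme participants, mostly with another explanation. As an illustration, 1% of 450 is 4.5 participants. This limits the importance of the point but also keeps the remedy small.

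A reader might infer two further consequences that the documents do not support:

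- *That late sampling is needed to recognise a partial intravenous injection.* Suspected maladministration has its own sample at 2 hours after dosing (6.7), and Section 2.3 expects concentrations to be lower, not higher, after the early peak.
- *That the restart decision depends on a PK value.* The visible text of 10.3.2 rests restart on a clear cause other than the study drug. Concentration is not a visible criterion, and nearby text is blacked out.

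**Conclusion.** The point holds as a defect in a stated rule and a contradiction between sections. The 60-hour limit covers daily oral dosing completely, about 8% of the Dose 1–2 interval and about 4% of each two-month interval, for drugs the protocol describes as measurable beyond a year. Liver events outside the window may have no exposure measurement. That includes most events meeting the two-week persistence criterion, symptomatic events between visits, and events found at long-term follow-up visits.

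A reader might go on to infer that 96%, or most, liver events on long-acting drug will go unmeasured. The documents do not support that. It needs both even detection over the two-month interval and 10.3.1 overriding 8.4.4 and 8.6, and neither is established. The 4% and 8% are shares of time, and the share of events lost cannot be fixed without the laboratory turnaround and the pattern of detection.

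**What to change.** Reconcile 10.3.1 and footnote 4 with 8.4.4 and 8.6:

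- Limit the 60-hour restriction to oral dosing (lead-in and oral bridging in participants not yet injected, or where the oral dose is the one of interest).
- For participants who have received any CAB LA or RPV LA injection, remove the instruction not to sample. Take the PK sample at the liver-event follow-up visit whatever the time since injection.
- Record the date and time of both the last injection and the draw, so that the value can be interpreted.

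This is a short wording change about data collection. It alters no dose, stopping or restart rule. The cost is one extra tube and assay for a small number of events, at a visit where blood is already being taken for repeat liver chemistry.
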